Many long-term side effects of therapy cause significant morbidity and mortality [2]. One problematic long-term side effect of therapy is the irreversible ototoxicity due to platinum-based chemotherapy [16, 17] that is estimated to occur in up to 61% of patients receiving cisplatin and postulated to be due to cochlear oxidative damage [3-5, 16]. Ototoxicity negatively impacts patients' quality of life by impairing their social and cognitive function and overall development [5]. It can also indirectly lead to increased risk of cancer recurrence if the cumulative dose of cisplatin is significantly reduced due to ototoxicity [5]. Cardiac toxicity caused by anthracycline-induced oxidative damage is another common dose-limiting side effect of therapy [18, 19]. Up to 40% of patients who receive anthracyclines will have an abnormal echocardiogram and survivors of childhood cancers who were treated with anthracyclines have a 15-fold increased relative risk of congestive heart failure compared to adults who were not treated for a childhood cancer [2]. Such therapy-related toxicities significantly impact patients' quality of life and cause treatment-related mortalities. Therapies that limit normal tissue damage without negatively impacting the therapeutic effects of chemotherapy and radiation are needed to improve outcomes and quality of life for childhood cancer patients.

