4.7.2 Genistein/Placebo Supplementation

For the purposes of this study, the duration of treatment cycles will coincide exactly with chemotherapy cycles. "Cycle 1" here refers to the first chemotherapy cycle during which the subject receives genistein or placebo, though this may not be the actual first cycle of the subject's chemotherapeutic treatment.

Subjects will receive 30 mg genistein (Arm A) or placebo (Arm B) daily throughout Cycles 1 & 2, beginning on the first day of the first cycle of chemotherapy coinciding with this study (Cycle 1 Day 1) and ending two days prior to the predicted start date of Cycle 3. Following a 2-day washout, subjects will then receive placebo (Arm A) or 30 mg genistein (Arm B) throughout chemotherapy Cycles 3 & 4, beginning on the first day of Cycle 3 and ending on the last day of Cycle 4. **The treatment schedule is summarized on Roadmaps, located in the Procedure Manual appendices.** For the purposes of this clinical trial, “study supplement” will refer to both genistein and placebo.

The study supplement will be delivered orally by the subject or a parent, and a diary will be kept to document dose administration. For doses given at home, subjects and parents will be instructed to bring unused pills to study visits. For children who are unable to swallow tablets, instructions for crushing and administering will be given to the families (Procedure Manual). Tablets may be crushed and delivered via feeding tube only if subjects are unable to take the medication orally and the feeding tube terminates in the stomach. Delivery to the duodenum or jejunum may alter genistein pharmacokinetics.

Subjects will record study treatments on a daily Pill Diary to indicate number of doses and time of dosing (Procedure Manual). If a subject misses a dose by less than 12 hours, he or she must be instructed to take the missed dose. If a subject misses a dose by more than 12 hours, he or she must be instructed to skip the missed dose and continue with regular dosing schedule. However, he or she must redose if vomiting occurs within the first 20 minutes after study supplement ingestion. Redosing may occur only once per 24 hour period.

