¹² CBC must be collected once during Baseline (Day -7 to 1), and then Day 1 of Cycles 2, 3, and 4, and Day 8 of Cycles 1, 2, 3, and 4. Once ANC begins to decrease each cycle, obtain twice a week until ANC recovery (see [Section 7.1](#) for definition of ANC recovery). CBC must include the following: hemoglobin, hematocrit, platelet count, total white blood cell count and automated differential (manual differential if automated not available).

¹³ Blood sample must be drawn at Baseline (Day -7 to Day 1), Day 1 of Cycles 2, 3, and 4, and the last day of Cycle 4.

¹⁴ Blood sample must be drawn on Day 1 of Cycles 1, 2, 3, and 4, and the last day of Cycle 4.

¹⁵ In subjects receiving platinum based chemotherapy only, an audiogram must be resulted at baseline (Day -7 to Day 1) and again 0 - 4 days prior to Day 1 of Cycles 2, 3, 4, and the last day of Cycle 4. If hearing loss is detected then adjust dose per [Section 4.7.4](#).

¹⁶ G-CSF, antimicrobials, blood product transfusions, anti-neoplastic agents, and soy-based products ([Section 4.8](#) and [6.4](#))

¹⁷ Concomitant medications used in the 28 days prior to the initiation of the study intervention

¹⁸ Dispense Day 1 of each cycle. Weekly review recommended but not required. Collect and review on the last day of each cycle.

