6.3 Treatment Phase Assessments (Cycles 1 – 4)

Investigators should maintain good clinical practice and perform standard of care assessments and procedures per local institutional guidelines. In addition, the following list of study-specific assessments must be performed once a patient enters the Treatment Phase. All visits and assessments must be completed within \pm 72 hours of the milestone date unless otherwise specified.

- The following will be performed for the purposes of assessing clinically significant AEs. AEs found prior to the first study supplement dose must be reported as baseline conditions. See [Section 9](#) and the Procedure Manual for more information about AE reporting.
 - Chemistry/metabolic liver function labs on Day 1 of each cycle: must include serum creatinine, total bilirubin, AST, and ALT (Procedure Manual)
 - CBC with differential on Day 1 of Cycles 2, 3, and 4, and at weekly visits: must include hemoglobin, hematocrit, platelet count, total white blood cell count and automated white blood cell differential (manual differential if automated not available) (Procedure Manual). See below for additional requirements for ANC reporting.
 - Full physical exam on Day 1 of each cycle and a symptom-directed physical exam at each of the weekly visits ([Section 6.2.1](#))
 - The Pre-treatment and Cycle 1 Day 1 physical exams may be combined performed \leq 72 hrs. prior to Cycle 1 Day 1.
 - Subjects receiving vincristine must be assessed for vincristine toxicity in the form of peripheral motor neuropathy.
 - Audiograms for subjects receiving a platinum-based chemotherapy agent at 0 - 4 days prior to Day 1 of Cycles 2, 3, 4, and 0 - 4 days prior to the last day of Cycle 4. Assess hearing impairment and tinnitus.
- ANCs must be obtained as follows:
 - The ANC must include both neutrophils and bands. The following equation is recommended:
$$\text{ANC} = \text{WBC} \times 1000 (\% \text{ Neutrophils} + \% \text{ Bands})$$
 - Obtain on Day 1 of Cycles 2, 3, 4 and at weekly visits

- Once ANC levels begin to decrease, ANC must be determined at least twice weekly (≤ 96 hours between blood collection) until ANC recovers to ≥ 500 cells/ μ L, then switch to weekly testing in the following situations:
 - If nadir is < 500 cells/ μ L, begin once ANC ≥ 500 cells/ μ L, OR
 - If nadir is ≥ 500 cells/ μ L, begin once ANC has increased by 50% above nadir

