- If ANC is < 500 cells/ μ L at any point after beginning weekly testing, resume twice weekly testing until ANC ≥ 500 cells/ μ L.
- ANC will be obtained daily during any admission for febrile neutropenia.
- All ANC values will be reported.
- Serum CRP, homocysteine, and ESR: Report raw data collected on Day 1 of Cycles 2, 3, 4, and the last day of Cycle 4
- Cytokine Panel and Isoflavone Panels: Draw and process specimen per the Procedure Manual on Day 1 of Cycles 1, 2, 3, 4, and the last day of Cycle 4
- Weight and height on Day 1 of each cycle
- The following **target AEs** must be assessed and the maximum grade reported for each cycle in addition to standard AE/SAE reporting ([Section 9](#)):
 - Neutropenia
 - Febrile neutropenia, with maximum associated temperature per cycle
 - Fever, including number of days per cycle, for temperatures $> 101.5^{\circ}$ F, or $> 100^{\circ}$ F more than once in a 24-hour period (report maximum temperature)
 - Infections and Infestations: Maximum grade for any AE listed in this CTCAE category. Infections meeting the AE reporting threshold must be listed individually.
 - Oral mucositis
 - Tinnitus (subjects receiving platinum-based chemotherapy only)
 - Hearing impairment (subjects receiving platinum-based chemotherapy only)
 - Peripheral motor neuropathy (subjects receiving vincristine only)
- Report per cycle:
 - Study supplement:
 - Total number of tablets taken

- Subject compliance with study medication dosing as determined by self-reported administration reports and supplement reconciliation
- Reason for dose change, if applicable. Any AE(s) precipitating a dose reduction must be reported even the minimum AE reporting threshold is not otherwise met ([Section 9.2](#)).
- Anti-neoplastic treatment delay(s):
 - Total number of days delayed from planned schedule
 - Cause for delay: AE, or reason other than AE
- Anti-neoplastic agent dose reduction(s):
 - Delayed agent(s)
 - Planned dose(s)
 - Actual dose(s)
 - Cause for dose change: AE, or reason other than AE
- All unplanned or prolonged hospitalizations due to (an) AE(s) ([Section 9.1.9](#)):
 - Date of admission or start of prolongation and discharge date
 - Causes/diagnoses precipitating hospitalization or prolonged hospitalization
- Concomitant medication review at each scheduled visit for the following:

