8.4 Data Analyses Plans

Graphical and repeated measure models will be used to describe the complete pattern of ANC over all four cycles. Between-group (Cycles 1 & 2) and crossover differences (Cycles 1 - 4) form the structure for treatment comparisons. Repeated measure models

will be used to assess differences in raw ANC, daily ANC, days with fever, duration of hospitalization, and duration of antimicrobial use for subjects admitted with febrile neutropenia. The Cochran–Mantel–Haenszel test statistics will be used in the analysis of stratified categorical data such as neutropenia grades (severe: ≤ 100 cells/ μl ; moderate: ≤ 500 cells/ μl ; mild: ≤ 1000 cells/ μl) and filgrastim (G-CSF) usage. For duration and severity of mucositis and peripheral motor neuropathy, detailed physical examinations will be documented at each weekly physical exam. Grading (grade 1 - 5) will be performed according to the [CTCAE](#) guidelines, version 4.0. The Cochran–Mantel–Haenszel test will be used to compare grade and repeated measure models for duration of mucositis between cycles containing genistein versus placebo.

Number of subjects who experience hearing impairment and tinnitus will be summarized by treatment for each cycle. The number of required blood product transfusions, both packed red blood cells and platelets, will be documented and compared during genistein and placebo cycles using repeated measure models. Reporting will be in the form of total ml/kg body weight infused of red blood cells and platelets. Criteria for transfusion are listed in [Section 4.8.2](#).

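### The per-cycle count of hearing impairment by treatment carries irreversible losses from Cycles 1-2 into the other treatment's column in Cycles 3-4

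*Combined protocol and SAP*

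**What the plan says.** - **Analysis (8.4).** "Number of subjects who experience hearing impairment and tinnitus will be summarized by treatment for each cycle". No test or model is named for this summary. The same section bases treatment comparisons on the between-group contrast in Cycles 1-2 and on crossover differences over Cycles 1-4.
- **Endpoint (Synopsis and 7.2).** Incidence and severity of hearing impairment and tinnitus, in platinum-treated subjects, are a secondary endpoint. The Synopsis says the listed endpoints are compared between cycles on genistein and cycles on placebo. Section 7.2 lets incidence mean the number of affected subjects and does not restrict it to new cases.
- **Data (6.3).** Hearing impairment and tinnitus are target adverse events, which "must be assessed and the maximum grade reported for each cycle in addition to standard AE/SAE reporting".
- **Audiograms.** Table 3, footnote 15: "an audiogram must be resulted at baseline". Section 6.3 adds: "Audiograms for subjects receiving a platinum-based chemotherapy agent at 0 - 4 days prior to Day 1 of Cycles 2, 3, 4", and again before the last day of Cycle 4.
- **Crossover (4.7.2).** "Following a 2-day washout, subjects will then receive placebo (Arm A) or 30 mg genistein (Arm B) throughout chemotherapy Cycles 3 & 4".
- **Nature of the outcome (1.2.1).** "One problematic long-term side effect of therapy is the irreversible ototoxicity due to platinum-based chemotherapy", a toxicity "that is estimated to occur in up to 61% of patients receiving cisplatin".

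**The concern.** A crossover contrast assumes that the outcome can return to its starting state before the second period. A 2-day washout may clear the supplement, but it cannot restore hearing that has been lost. A subject in Arm B whose loss began on placebo in Cycle 1 will still have a graded impairment in Cycles 3 and 4, when the subject sits in the genistein column. Arm A does the same in the other direction.

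Nothing in the plan limits the count to new onset or worsening, resets the reference at Cycle 3, or confines the hearing comparison to Cycles 1-2. At stake is how half the rows of this table are read, together with any genistein-versus-placebo figure pooled over all four cycles.

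**Working it through.** **Inputs.** The documents give no per-cycle risk of hearing loss, no assumed genistein effect on hearing, and no size for the platinum subset, so there is no planned figure to reproduce. The only rate is the 61% upper figure for cisplatin in 1.2.1. The following are my assumptions: constant risk per cycle, no recovery, equal arms, placebo risk p, and genistein risk g = p/2.

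**Formulas.** Write a = 1 - p and b = 1 - g. Arm A runs genistein, genistein, placebo, placebo; Arm B runs placebo, placebo, genistein, genistein. The proportion affected in each cycle is:

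| Cycle | Genistein column | Placebo column |
|---|---|---|
| 1 | 1 - b (Arm A) | 1 - a (Arm B) |
| 2 | 1 - b² (Arm A) | 1 - a² (Arm B) |
| 3 | 1 - a²b (Arm B) | 1 - b²a (Arm A) |
| 4 | 1 - a²b² (Arm B) | 1 - b²a² (Arm A) |

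The Cycle 3 difference, genistein minus placebo, is ab(p - g). It is positive whenever genistein protects. The Cycle 4 difference is exactly zero for any p and g, because each arm has by then had two cycles of each treatment.

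**Numbers.**

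| Cycle | p = 0.10, g = 0.05 | Difference | p = 0.20, g = 0.10 | Difference |
|---|---|---|---|---|
| 1 | 5.0% vs 10.0% | -5.0 | 10.0% vs 20.0% | -10.0 |
| 2 | 9.75% vs 19.0% | -9.2 | 19.0% vs 36.0% | -17.0 |
| 3 | 23.05% vs 18.8% | +4.3 | 42.4% vs 35.2% | +7.2 |
| 4 | 26.9% vs 26.9% | 0 | 48.2% vs 48.2% | 0 |

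Cycle 3 check at p = 0.10: 0.90 × 0.95 × 0.05 = 0.043.

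**Pooling.** At p = 0.10 the four-cycle average is 16.2% on genistein (64.7/4) against 18.7% on placebo (74.7/4). The ratio is 0.87, where the true per-cycle ratio is 0.5.

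**Where the Cycle 3 cases come from.** At p = 0.10, 19.0/23.05 = 82% of those in the genistein column began under placebo, and 9.75/18.775 = 52% of those in the placebo column began under genistein.

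**Range.** The two scenarios imply four-cycle placebo risks of 1 - 0.9⁴ = 34% and 1 - 0.8⁴ = 59%. With four-cycle placebo risks of 20%, 40% and 61%, again halving the per-cycle risk, the Cycle 3 difference is +2.5, +5.0 and +7.4 points. Cycle 4 stays at zero.

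**Counting first onset instead.** At p = 0.10, Cycle 3 becomes 0.81 × 0.05 = 4.05% on genistein against 0.9025 × 0.10 = 9.0% on placebo. Cycle 4 becomes 0.7695 × 0.05 = 3.8% against 0.81225 × 0.10 = 8.1%. The direction is right in every cycle.

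**No true effect.** If g = p, the two columns agree in expectation in every cycle. Carry-over still supplies most of the Cycle 3 count (19.0/27.1 = 70% at p = 0.10), but evenly on both sides.

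**The case against.** The best counter-argument is that the summary may be meant as a count of new events. Section 9.1.2 logs a persistent adverse event once, at its initial grade, and opens a separate entry only on worsening. Section 9.1.1 requires onset dates. A table built from those entries would place a stable Cycle 2 loss in Cycle 2 only. This reading is possible, but the plan does not state it. Section 9.1.2 governs adverse event entries and is not linked to the hearing summary, while 6.3 asks for a per-cycle maximum grade on top of that standard reporting.

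The second objection is that the table is descriptive and laid out cycle by cycle. This stands in part. Within Cycles 1 and 2, treatment is the randomized arm, so those rows show any effect cleanly. A reader might infer that the whole table is invalid or that it conceals a protective effect. The documents do not support that: the Cycle 2 row would display it, and no hearing-specific test or pooled contrast is named. What remains is that the Synopsis and the general structure in 8.4 invite a contrast over all four cycles.

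Third, the size is assumed and small in subjects. Even if all 22 subjects per group received platinum, +4.3 points is 0.95 of a subject and +7.2 points is 1.6; the actual subset may be smaller. A reader might also infer that carry-over manufactures a treatment difference from nothing. It does not, since without a true effect it is balanced in expectation.

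Fourth, 1.2.1 calls ototoxicity irreversible but does not say so separately of tinnitus. The argument is firm for hearing impairment only.

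**Conclusion.** The concern holds in a limited form. As written, the by-treatment count carries irreversible hearing loss across the swap, so the Cycle 3-4 rows and any contrast pooled over Cycles 1-4 do not measure the effect of the treatment heading the column. With a real effect, the Cycle 3 contrast can reverse (+4.3 to +7.2 points in the main illustration) and the Cycle 4 contrast vanishes. The direction of the distortion follows from the design under constant per-cycle risk and no recovery; its size rests on the assumed rates and the assumed halving.

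The Cycle 1-2 rows are unaffected. This is an untested secondary summary in a platinum subset of unstated size, so the point is a worthwhile correction to the analysis wording and does not threaten the trial's main conclusions.

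**What to change.** Amend 8.4 as follows:

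1. Count hearing impairment in a cycle only if it is new, or worse in grade, relative to the audiogram that opens the period: the baseline audiogram for Cycles 1-2 and the pre-Cycle 3 audiogram for Cycles 3-4.
2. Name the between-arm contrast in Cycles 1-2 as the treatment comparison for hearing.
3. Show Cycles 3-4 descriptively by sequence (Arm A, Arm B). Even new-onset counts there come from groups whose numbers still at risk already depend on the earlier treatment.
4. For tinnitus, apply the same rule of new onset or worsening, using the clinical grade at the start of each period, since an audiogram does not supply that reference.
5. State whether the record-once rule in 9.1.2 or the per-cycle maximum grade in 6.3 feeds this table.

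The audiograms are already scheduled and the Cycle 1-2 contrast is already part of the plan, so no visit or data item is added. The cost is that the treatment comparison for hearing uses two cycles instead of four.

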9 ADVERSE EVENTS AND REPORTING

After informed consent has been obtained but prior to initiation of investigational intervention, only SAEs caused by a protocol-mandated intervention must be reported (e.g. SAEs related to invasive procedures).

After initiation of the investigational study supplement dosing, all AEs must be collected as described in the following sections through 30 days after the last study supplement dose ([Section 6](#)). In addition, investigators must report any deaths, SAEs, other AEs of concern that are believed to be related to the investigational intervention, cancer progression, cancer relapse, and secondary malignancies through six months after the end of the study intervention. See the Procedure Manual for additional information on and resources for AE reporting.

All AEs, whether reported by the subject or noted by study personnel, must be recorded in the subject's medical and study records. AEs must be assessed for seriousness, severity, attribution and expectedness by the investigator. The following sections provide definitions for AE characteristics and reporting requirements.

AEs must be followed to resolution or stabilization, and reported as SAEs if they are or become serious. This also applies to subjects experiencing AEs that cause interruption or discontinuation of study intervention, or those experiencing AEs that are present at the end of their participation in the study. Such subjects should receive post-treatment follow-up as appropriate.

If an ongoing AE changes in its severity or in its perceived relationship to study intervention, a new AE entry for the event must be completed.

9.1 Definitions

9.1.1 Adverse Event [72]

An adverse event is any untoward medical occurrence in a subject who has received an investigational intervention, whether or not related to the investigational intervention(s). Medical conditions present before starting the investigational intervention (pre-existing conditions) will be considered AEs only if they worsen after starting the study supplement ([Sections 6.3](#) and [9.1.6](#)). AEs include unfavorable, harmful or pathological changes in the general condition of a subject; subjective or objective symptoms (spontaneously offered by the subject and/or observed by the Investigator or the study nurse); intercurrent events or exacerbation of pre-existing diseases which occurred after the administration of the study supplement; clinically significant changes in laboratory abnormalities; or any undesirable and unintended effect of research occurring in human subjects as a result of the collection of identifiable, private information for research purposes.

Only clinically significant AEs will be reported on this study. Reporting will include, at minimum, the dates of onset and resolution, severity, attribution to study intervention, expectedness, seriousness, and treatment (medication, transfusion, procedure, other, or none). AEs should be reported as diagnoses, when possible.

9.1.2 Persistent or Recurrent Adverse Events

A persistent AE is an event which extends continuously, without resolution, between assessments. This event must only be recorded once with the initial severity grade. If the severity of the event worsens, then the original event ends and a separate event is recorded at the greater grade or with an altered relationship to the study supplement.

A recurrent AE is an event which resolves between assessments and subsequently recurs. This must be recorded as a separate event for each recurrence.

9.1.3 Secondary Adverse Events

In general, events occurring secondary to other events (e.g., cascade events or clinical sequelae) must be considered a single event identified by the primary cause. However, a secondary event must be listed as an independent event if it meets one of the following criteria:

- Severe
- Serious
- Separated in time from the primary event

If it is not clear as to whether events are dependent, then record as separate AEs.

9.1.4 Abnormal Laboratory Values/Clinical Assessments

It is the responsibility of the investigator to review and document all laboratory findings and clinical assessments, which may include vital signs, physical exams and electrocardiograms (ECGs). Medical and scientific judgment must be exercised in deciding whether a laboratory abnormality or clinical finding must be classified as an AE. An abnormal laboratory test result or clinical finding must be considered as an AE if it meets at least one of the following criteria:

- Is associated with clinical symptoms
- Results in a change in study treatment (e.g., treatment modification, interruption or discontinuation)
- Requires a medical intervention or change in concomitant therapy
- Clinically significant in the investigator's judgment

